4.3. Lifestyle Requirements

4.3.1. Contraception

Lorlatinib is teratogenic and an aneugen and can therefore cause harm when administered to a pregnant woman. Therefore, use of an appropriate method of contraception during treatment with these study drugs is mandatory.

The investigator or his or her designee, in consultation with the participant, will confirm that the patient has selected a highly effective method of contraception for the individual patient and his or her partner(s) from the permitted list of contraception methods (see below) and will confirm that the participant has been instructed in its consistent and correct use. At time points indicated in the [schedule of activities](#), the investigator or designee will inform the patient of the need to use a highly effective method of contraception consistently and correctly and document the conversation and the participant's affirmation in the patient's chart (patients need to affirm their consistent and correct use of at least one of the appropriate methods of contraception).

In addition, the investigator or designee will instruct the participant to call immediately if the selected contraception method is discontinued or if pregnancy is known or suspected in the participant or partner.

Women of childbearing potential (WOCBP, definition provided below, [Section 4.3.1.1](#)) must agree to use a highly effective nonhormonal method of contraception, because lorlatinib can render hormonal contraceptives ineffective. If a hormonal method of contraception is unavoidable, then a condom must be used in combination with the hormonal method. Contraception must be continued for at least 21 days after completing therapy.

During treatment with lorlatinib and for at least 97 days after the final dose, male patients with WOCBP partners must agree to use a highly effective method of contraception, including a condom, and male patients with pregnant partners must be agreed to use condoms (see [Section 4.3.1.2](#)).

All sexually active male patients must agree to prevent potential transfer to and exposure of pregnant partner(s) and fetus to drug through ejaculate by using a condom consistently and correctly, beginning with the first dose of lorlatinib and continuing for at least 97 days after the last dose of lorlatinib.

In addition, the investigator or designee will instruct the patient to call immediately if the selected contraception method is discontinued or if pregnancy is known or suspected in the participant or partner.

4.3.1.1. Woman of Childbearing Potential (WOCBP)

A woman is considered fertile following menarche and until becoming postmenopausal unless permanently sterile (see below).

If fertility is unclear (eg, amenorrhea in adolescents or athletes) and a menstrual cycle cannot be confirmed before the first dose of study intervention, additional evaluation should be considered.

Women in the following categories are not considered WOCBP:

1. Premenopausal female with 1 of the following:
 - Documented hysterectomy;
 - Documented bilateral salpingectomy;
 - Documented bilateral oophorectomy;
 - For individuals with permanent infertility due to an alternate medical cause other than the above, (eg, mullerian agenesis, androgen insensitivity), investigator discretion should be applied to determining study entry;
 - Note: Documentation for any of the above categories can come from the site personnel's review of the participant's medical records, medical examination, or medical history interview. The method of documentation should be recorded in the participant's medical record for the study.

2. Postmenopausal female:

A postmenopausal state is defined as age 60 years or older or no menses for 12 months without an alternative medical cause.

 - A high follicle-stimulating hormone (FSH) level in the postmenopausal range may be used to confirm a postmenopausal state in women not using hormonal contraception or hormone replacement therapy (HRT).

Females on HRT and whose menopausal status is in doubt will be required to use one of the nonhormonal appropriate contraception methods if they wish to continue their HRT during the study. Otherwise, they must discontinue HRT to allow confirmation of postmenopausal status before study enrollment.

4.3.1.2. Methods of Contraception

1. Established use of oral, inserted, injected or implanted hormonal methods of contraception are allowed provided a condom is used in combination with the hormonal method. The patient must have been using that hormonal contraceptive for an adequate period of time to ensure effectiveness.
2. Correctly placed copper-containing intrauterine device (IUD).
3. Bilateral tubal ligation/bilateral salpingectomy or bilateral tubal occlusive procedure (provided that occlusion has been confirmed in accordance with the device's label).
4. Male condom must be used in association with a female highly effective method of contraception.
5. Male sterilization with absence of sperm in the postvasectomy ejaculate.

NOTE: For patients not sexually active, sexual abstinence, defined as completely and persistently refraining from all heterosexual intercourse (during the entire period of risk associated with the study treatments) may obviate the need for contraception ONLY if this is the preferred and usual lifestyle of the subject. Investigator should assess at each visit if a change of patient lifestyle occurred and in case reconsider, in consultation with the patient, to select an appropriate methods of contraception for the individual patient and his/her partner(s) from the list of permitted contraception methods.

4.4. Sponsor's Qualified Medical Personnel

The contact information for the sponsor's appropriately qualified medical personnel for the study is documented in the study contact list located in the study manual.

To facilitate access to appropriately qualified medical personnel on study-related medical questions or problems, subjects are provided with a contact card. The contact card contains, at a minimum, protocol and investigational product identifiers, subject study numbers, contact information for the investigator site, and contact details for a contact center in the event that the investigator site staff cannot be reached to provide advice on a medical question or problem originating from another healthcare professional not involved in the subject's participation in the study. The contact number can also be used by investigator staff if they are seeking advice on medical questions or problems; however, it should be used only in the event that the established communication pathways between the investigator site and the study team are not available. It is therefore intended to augment, but not replace, the established communication pathways between the investigator site and the study team for advice on medical questions or problems that may arise during the study. The contact number is not intended for use by the subject directly, and if a subject calls that number, he or she will be directed back to the investigator site.

5. STUDY TREATMENTS

For the purposes of this study, and per International Conference on Harmonisation (ICH) guidelines, investigational product is defined as a pharmaceutical form of an active ingredient or placebo being tested or used as a reference/comparator in a clinical trial, including a product with a marketing authorization when used or assembled (formulated or packaged) in a way different from the approved form, or when used for an unapproved indication, or when used to gain further information about an approved use (ICH E6 1.33).

For this study, the investigational product(s) is lorlatinib (PF-06463922).

5.1. Allocation to Treatment

The investigator's knowledge of the treatment should not influence the decision to enroll a particular subject or affect the order in which subjects are enrolled.

A subject must sign an informed consent document (ICD) before being evaluated for study entry. Once a subject who has met inclusion and exclusion criteria has provided a signed ICD, allocation of subjects to lorlatinib treatment will proceed through the use of an interactive response technology (IRT) system (interactive Web-based response [IWR]). The site personnel (study coordinator or specified designee) will be required to enter or select information including but not limited to the user's identification (ID) and password, the protocol number, and the subject number. The site personnel will then be provided with a treatment assignment, randomization number, and dispensable unit (DU) or container number when investigational product is being supplied via the IRT system. The IRT system will provide a confirmation report containing the subject number, randomization number, and DU or container number assigned. The confirmation report must be stored in the site's files.

The study-specific IRT reference manual will provide the contact information and further details on the use of the IRT system.

Qualified subjects will be enrolled to the study to receive lorlatinib monotherapy at the RP2D of 100 mg QD, administered as 4×25 mg oral tablets, continuously. Study treatment should be initiated preferably on the randomization day but no later than 1 day after randomization.

5.2. Subject Compliance

For self-administration of lorlatinib at home, compliance will be captured and completed by the subject.

A patient diary will be provided to the subjects to aid in lorlatinib compliance. The diary will be maintained by the subject to include unchanged, missed, or changed doses.

Subject will be required to return to the investigational site all bottles of lorlatinib at the end of each 21-day cycle during the planned visit at the site. The number of lorlatinib tablets remaining will be documented and recorded at each clinic visit.

The study site must follow up (for example, via a telephone call) with each subject on Cycle 1 Day 5 (± 3 days) to confirm that the subject understands and is in compliance with lorlatinib dosing instructions. If needed, the subject will be re-trained. The same follow-up process will be applied in case the dose of lorlatinib is modified during the treatment period.

5.3. Investigational Product Supplies

5.3.1. Dosage Form(s) and Packaging

Lorlatinib will be supplied for oral administration as 25 mg tablets in High-Density Polyethylene (HDPE) bottles with desiccant and labeled according to local regulatory requirements.

5.3.2. Preparation and Dispensing

Only qualified personnel who are familiar with procedures that minimize undue exposure to themselves and to the environment should undertake the preparation, handling, and safe disposal of investigational agents. Investigational product should be prepared and dispensed by an appropriately qualified and experienced member of the study staff (eg, physician, nurse, physician's assistant, nurse practitioner, pharmacy assistant/technician, or pharmacist) as allowed by local, state, and institutional guidance.

Lorlatinib will be dispensed at the beginning of every 21-day cycle (or as otherwise indicated) using an IRT drug management system. Subjects should be instructed to keep their medication in the bottles provided and not transfer it to any other container. Lorlatinib will be provided in bottles containing 25 mg tablets. Site personnel must ensure that subjects clearly understand the directions for self-medication. Subjects should be given sufficient supply to last until their next study visit. Subjects will be provided with Drug Administration Cards and Patient Diaries. In addition, administration instructions will be detailed for site personnel in the Investigational Product (IP) Manual.

5.4. Administration

All study treatments will be administered on an outpatient basis.

A cycle is defined as 21 days, irrespective of any dose delays/dosing interruptions or missed doses which may affect nominal days of each cycle.

Lorlatinib will be administered orally QD at approximately the same time of the day on a continuous daily dosing schedule, ie, without a break in dosing in the absence of drug-related toxicity. Subjects will swallow the investigational product whole, and will not manipulate or chew the investigational product prior to swallowing. A dosing card will be provided to the subjects to provide guidance for the correct use of lorlatinib. Subjects must be instructed that should they miss a dose or vomit any time after taking a dose, they must not "make it up" with an extra dose. Instead, resume the subsequent doses as originally prescribed. Any missed dose may be taken up to 6 hours prior to the next scheduled dose, otherwise it should be skipped and dosing resumed with subsequent doses as prescribed. The subject must be instructed to record all doses (including missed or vomited) in a dosing diary supplied by the site. If doses are missed or vomited, this must be indicated in the source documents and Case Record Forms (CRFs).

On PK sampling days, the lorlatinib dose should be taken in the clinic under the supervision of the study site personnel. The lorlatinib dose should be administered after the 0 hour (predose) PK sample has been collected.

Since no clinically meaningful effect of food on the PK of lorlatinib has been observed, lorlatinib can be administered with or without food.

5.4.1. Treatment duration

The study treatment may continue until disease progression confirmed by independent central radiology (ICR) review, unacceptable toxicity, subject lost to follow-up, or subject refusal, or the study is terminated by the sponsor, whichever comes first.

If the subject has documented PD by ICR, subjects should be discontinued from study treatment. However, if according to the investigator's clinical judgment and after discussion between the investigator and Pfizer, if a subject with evidence of PD is still experiencing clinical benefit, the subject may be eligible for continued lorlatinib treatment. The investigator's judgment should be based on the overall benefit/risk assessment and the subject's clinical condition, including ECOG performance status, clinical symptoms, adverse events and laboratory data.

5.5. Recommended Dose Modifications

Every effort should be made to administer investigational products on the planned dose and schedule. In the event of significant toxicity, dosing may be delayed and/or reduced as described below. In the event of multiple toxicities, dose modification should be based on the worst toxicity observed. Subjects are to be instructed to notify their investigators at the first occurrence of any adverse event.

If a dosing interruption longer than 4 weeks due to ongoing treatment-related toxicity is necessary, study treatment should be permanently discontinued, unless there is a discussion of the clinical circumstance with the sponsor's medical monitor and agreement that the subject may resume treatment after a lapse of greater than 4 weeks.

In case of adverse events, investigators are encouraged to employ best supportive care according to local institutional clinical practices or follow the guidance for selected adverse events provided in [Table 2](#). Subjects will be monitored closely for toxicity, and the dose of lorlatinib may be adjusted as indicated in [Table 1](#) below. All dose modifications will be reported in the Case Report Form (CRF).

Table 1. Lorlatinib Dose Levels for Inpatient Dose Modifications

Dose Levels	Lorlatinib dose
0	100 mg QD
-1	75 mg QD
-2	50 mg QD

Dose reductions below dose level -2 are not allowed.

Inpatient dose reduction by 1 and, if needed, 2 dose levels will be allowed depending on the type and severity of toxicity encountered (Dose Level -1 is 75 mg QD; Dose Level -2 is 50 mg QD). It is recommended that in case of lorlatinib dose decrease, the subject is assigned new drug rather than using less tablets from the bottle assigned at previous visit.

If a subject has a significant toxicity from lorlatinib treatment which fails to recover within 28 days (4 weeks) or, in the opinion of the investigator, requires permanent discontinuation of the treatment based on the severity of the adverse event, then this subject should not be further treated with lorlatinib but should remain in the study with ongoing tumor assessments until RECIST-defined disease progression by the ICR.

Recommendations for lorlatinib dose modification for treatment-related non-hematological and hematological toxicity, as well as for treatment-related toxicity of special interest, are provided in Table 2 below.

Re-escalation is not allowed except if discussed with and approved by the sponsor’s medical contact.

Table 2. Lorlatinib Dose Modifications for Lorlatinib-Related Toxicities

Toxicity	Grade 1**	Grade 2**	Grade 3	Grade 4
Non-Hematologic Toxicities				
Pancreatitis	NA	
If elevated enzymes (both amylase and lipase are Grade ≤ 2) are observed in the absence of radiological findings of pancreatitis: continue lorlatinib at the same dose level without dose hold. Repeat lipase and amylase and obtain pancreatic isoenzyme if possible.
 
If radiologically confirmed pancreatitis: withhold lorlatinib dose. Repeat radiology and lipase and amylase weekly and obtain pancreatic isoenzyme. If appropriate, resume lorlatinib treatment at one dose level lower if radiology has returned to baseline and lipase and amylase are Grade ≤ 2.
	Permanently discontinue lorlatinib	Permanently discontinue lorlatinib

Table 2. Lorlatinib Dose Modifications for Lorlatinib-Related Toxicities

Toxicity	Grade 1**	Grade 2**	Grade 3	Grade 4
Pneumonitis (in the absence of disease progression, pulmonary embolism, positive cultures or radiation effect) section	Asymptomatic, radiographic findings only: No need for lorlatinib dose adjustment. Initiate appropriate monitoring.	Withhold current lorlatinib dose until toxicity has returned to baseline. Rule out infection and consider initiating treatment with corticosteroids. Then resume lorlatinib treatment at one dose level lower. Discontinue lorlatinib permanently if pneumonitis recurs or if failure to recover after 6 weeks of study treatment hold and steroid treatment.	Permanently discontinue lorlatinib	Permanently discontinue lorlatinib
Electrocardiogram QTc prolongation (see Section 5.5.2)	Assess electrolytes and concomitant medications Correct any electrolyte abnormalities, or hypoxia Continue lorlatinib at the same dose level	Assess electrolytes and concomitant medications Correct any electrolyte abnormalities, or hypoxia Continue lorlatinib at the same dose level	Withhold lorlatinib dose Assess electrolytes and concomitant medications Correct any electrolyte abnormalities, or hypoxia. Upon recovery to Grade ≤ 1 resume lorlatinib treatment at one dose level lower.	Permanently discontinue lorlatinib
LV Dysfunction	CTCAE v4.03 does not report Grade 1.	CTCAE v 4.03 does not report Grade 2	Permanently discontinue lorlatinib	Permanently discontinue lorlatinib
Non-Hematologic General	Continue lorlatinib at the same dose level	Continue lorlatinib at the same dose level	Withhold lorlatinib dose until toxicity is Grade ≤ 1 (or has returned to baseline) then reduce the dose by 1 level or rechallenge at the same dose*	Withhold dose until toxicity is Grade ≤ 1 (or has returned to baseline), then reduce the dose by 1 level* or discontinue at the discretion of the investigator

Table 2. Lorlatinib Dose Modifications for Lorlatinib-Related Toxicities

Toxicity	Grade 1**	Grade 2**	Grade 3	Grade 4

* Subjects who develop asymptomatic Grade 4 hyperuricemia or Grade 3 hypophosphatemia may continue lorlatinib without dose modification at the discretion of the investigator. Nausea, vomiting or diarrhea must persist at Grade 3 or 4 despite maximal medical therapy to require lorlatinib dose modification.
 
** In cases where no specific dose adjustments for Grade 1 or Grade 2 treatment-related toxicity are provided, investigators should always manage their patients according to their medical judgment which may include dose reduction or interruption based on the particular clinical circumstances.
 
Section If a subject has a potential diagnosis of pneumonitis or drug-related lung injury the same evaluations/procedures provided in Section 5.5.3 should be considered to assist or exclude the diagnosis of pneumonitis during this period.
				
Hematologic Toxicities				
Hematologic General	Continue lorlatinib at the same dose level	Continue lorlatinib at the same dose level	Withhold lorlatinib dose until toxicity is Grade ≤1 (or has returned to baseline), then rechallenge at the same dose or reduce the dose by 1 dose level	Withhold lorlatinib dose until toxicity is Grade ≤1 (or has returned to baseline), then rechallenge at the same dose or reduce the dose by 1 dose level
Lymphopenia	Continue lorlatinib at the same dose level	Continue lorlatinib at the same dose level	If no evidence of infection or other clinically significant toxicity, continue lorlatinib at the same dose; otherwise, withhold dose until toxicity is Grade ≤1 (or baseline) then rechallenge at the same dose or reduce by 1 level	If no evidence of infection or other clinically significant toxicity, continue lorlatinib at the same dose; otherwise, withhold dose until toxicity is Grade ≤1 (or baseline) then rechallenge at the same dose or reduce by 1 level

Table 2. Lorlatinib Dose Modifications for Lorlatinib-Related Toxicities

Toxicity	Grade 1**	Grade 2**	Grade 3	Grade 4
Lipid Elevation Toxicities^a				
Cholesterol	
Continue lorlatinib at the same dose
 
Consider introducing use of a statin or other lipid lowering agent as appropriate based on investigator's medical judgment
	
Introduce the use of a statin or other lipid lowering agent as appropriate, and continue lorlatinib at the same dose
	
Introduce the use of a statin or other lipid-lowering agent as appropriate, or increase the dose of the statin/lipid lowering agent or change to a new agent. Continue lorlatinib at the same dose without interruption
	
Increase the dose of the statin or other lipid-lowering agent, or change to a new statin/lipid lowering agent. Withhold lorlatinib dose until toxicity is Grade ≤ 2
 
Re-challenge at same dose while maximizing lipid lowering therapy in accordance with respective prescribing information
 
If \geq Grade 3 hypercholesterolaemia recurs despite maximal lipid lowering therapy in accordance with respective prescribing information, reduce lorlatinib by 1 dose level

Triglycerides	
Continue lorlatinib at the same dose
 
Consider introducing use of a statin or other lipid lowering agent as appropriate based on investigator's medical judgment
	
Introduce the use of a statin or other lipid lowering agent as appropriate, and continue lorlatinib at the same dose
	
Introduce the use of a statin or other lipid-lowering agent as appropriate, or increase the dose of the statin/lipid lowering agent or change to a new agent. Continue lorlatinib at the same dose without interruption
	
Increase the dose of the statin or other lipid-lowering agent, or change to a new statin/lipid lowering agent. Withhold lorlatinib dose until toxicity is Grade ≤ 2
 
Re-challenge at same dose while maximizing lipid lowering therapy in accordance with respective prescribing information
 
If \geq Grade 3 hypertriglyceridaemia recurs despite maximal lipid lowering therapy in accordance with respective prescribing information, reduce lorlatinib by 1 dose level

Table 2. Lorlatinib Dose Modifications for Lorlatinib-Related Toxicities

Toxicity	Grade 1**	Grade 2**	Grade 3	Grade 4
^a See also instructions provided in Section 5.5.1 Hyperlipidemia				
CNS Toxicities				
Toxicity	Grade 1	Grade 2	Grade 3	Grade 4
CNS effects ^b	Continue lorlatinib at the same dose or withhold dose until recovery to baseline. Then resume at the same dose or reduce by 1 dose level	Withhold dose until toxicity is less than or equal to Grade 1. Then resume at 1 reduced dose level	Withhold dose until toxicity is less than or equal to Grade 1. Then resume at 1 reduced dose level	Permanently discontinue lorlatinib
^b Examples of CNS effects could include changes in speech, memory, sleep, cognition, or vision.				

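### For Grade 2 pneumonitis, Protocol Table 2 allows up to 6 weeks for recovery, while Section 5.5 sets 4 weeks (one statement with a medical monitor waiver, one without), and no text says which prevails

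*Protocol*

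**What the plan says.** Three pieces of text in Protocol Section 5.5 bear on a subject whose Grade 2 pneumonitis is attributed to lorlatinib.

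- **Table 2, pneumonitis row, Grade 2.** The first instruction is "Withhold current lorlatinib dose until toxicity has returned to baseline", followed by resumption one dose level lower. The stopping rule is "Discontinue lorlatinib permanently if pneumonitis recurs or if failure to recover after 6 weeks of study treatment hold and steroid treatment". The row does not mention the 4-week limit or the medical monitor.
- **Section 5.5, interruption paragraph.** "If a dosing interruption longer than 4 weeks due to ongoing treatment-related toxicity is necessary, study treatment should be permanently discontinued". The same sentence adds a waiver: a discussion with the sponsor's medical monitor and "agreement that the subject may resume treatment after a lapse of greater than 4 weeks".
- **Section 5.5, recovery paragraph after Table 1.** "If a subject has a significant toxicity from lorlatinib treatment which fails to recover within 28 days (4 weeks"), "then this subject should not be further treated with lorlatinib". This sentence has no waiver.

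Section 5.5 introduces the table by saying that recommendations for general toxicity, "as well as for treatment-related toxicity of special interest, are provided in Table 2 below". It does not say that the table overrides the 4-week statements, or the reverse. The footnote to the pneumonitis row points to Section 5.5.3, which describes the diagnostic work-up and sets no time limit.

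**The concern.** The same event has more than one stopping limit, and the limits come with different conditions. A site that works from the table would wait up to 6 weeks and resume without contacting the sponsor. A site that works from the text would stop at 4 weeks, or call the medical monitor, depending on the paragraph it reads.

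The decision is whether to re-expose a subject after lung toxicity. The study runs at approximately 30 sites (Section 3) without a data monitoring committee (Section 9.7), so like patients could be treated differently with no committee placed to notice.

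The SAP outputs that depend on the decision are descriptive:

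- discontinuations from study treatment, including those due to adverse events (6.4.2.1);
- treatment duration and dose intensity (6.4.3.1);
- dose reductions and interruptions (6.4.3.2);
- adverse events leading to interruption, reduction or withdrawal (6.5.1).

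**Working it through.** The protocol states no derived figure to reproduce. The check is a unit conversion and a side-by-side reading.

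**Inputs.** Table 2 limit: 6 weeks. Section 5.5 limits: 4 weeks of interruption, and 28 days to recover. For the comparison I assume that every clock starts on the first day of the hold. The recovery paragraph does not say when its 28 days begin.

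**Conversion.** 6 × 7 = 42 days. 4 × 7 = 28 days. Difference: 42 − 28 = 14 days, which is days 29 to 42 inclusive.

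**Does Section 5.5 reach this event?** Table 2 is titled for lorlatinib-related toxicities, so the event is treatment-related and the interruption paragraph applies directly. The recovery paragraph requires a significant toxicity, a term the protocol does not define. However, Section 5.5 opens by linking significant toxicity to dosing delay or reduction, and Table 2 prescribes both for this event. It plausibly qualifies, but the text does not settle the matter.

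**What each text says, by time of recovery**

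| Recovery to baseline | Table 2 row | Interruption paragraph | 28-day sentence (if significant) |
|---|---|---|---|
| By day 28 | Resume one level lower | No bar | No bar |
| Days 29 to 42 | Resume one level lower | Stop, unless the medical monitor agrees | No further lorlatinib |
| Not by day 42 | Stop permanently | Stop, unless the medical monitor agrees | No further lorlatinib |

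The middle row is the conflict. Against the interruption paragraph, the difference is whether sponsor agreement is needed. Against the 28-day sentence, the difference is resumption or no resumption. In the last row, the waiver has no stated upper limit while Table 2 stops outright, so the same reconciliation should cover it.

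**How many subjects.** The documents give no pneumonitis rate. As an illustration only, an assumed rate of 1% to 3% for pneumonitis of any grade gives 100 × 0.01 = 1 to 100 × 0.03 = 3 of the 100 planned subjects. That is a ceiling under the assumption. Grade 1 needs no dose change and Grades 3 and 4 are discontinued at once, so only Grade 2 cases recovering on days 29 to 42 count. The number may well be zero.

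**Do the efficacy analyses use the limit?** No.

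- Best overall response runs to progression or new anti-cancer therapy (SAP 6.1).
- The PFS censoring rules and reasons (SAP 6.2.6, Tables 2 and 3) do not include stopping lorlatinib.
- Scans continue until progression by central review after treatment stops (Protocol 5.5 and 7.1).
- The safety on-treatment period runs to the end of follow-up or new anti-cancer drug therapy, not to the last dose (SAP 3.5).

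**The case against.** The best defence is that a specific row governs over a general rule. Section 5.5 presents Table 2 as guidance for selected events, and pneumonitis has its own row, so its 6 weeks could be a deliberate exception. A joint reading of the row and the interruption paragraph also works: seek medical monitor agreement once the hold passes 4 weeks, and discontinue at 6 weeks without recovery. Both readings are reasonable, but neither is written down. Neither disposes of the 28-day sentence, which has no waiver and no exception for pneumonitis.

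A second objection is overlap. The two 4-week statements in Section 5.5 already differ from each other, and extending the waiver to the 28-day sentence would leave only a missing cross-reference in the Table 2 row. That is fair, and the two matters should be handled together. The row would still omit the agreement that the text requires.

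A reader might also infer more than the documents support:

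- **That Section 5.5 stops treatment for any toxicity unresolved at 28 days.** It is limited to significant toxicity from lorlatinib, or to ongoing treatment-related toxicity that causes an interruption.
- **That every subject in the window receives opposite instructions.** That is true only against the 28-day sentence. The interruption paragraph permits resumption with agreement.
- **That efficacy results are affected because later scans fall on or off drug.** The response and PFS rules do not depend on that status. What remains is any effect on the tumour itself, or an earlier switch to another therapy, in very few subjects.

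**Conclusion.** The protocol is internally inconsistent on this point and needs correction. For a subject with lorlatinib-related Grade 2 pneumonitis who recovers on days 29 to 42 of the hold, the row and the two paragraphs give three different answers, and nothing ranks them.

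The finding that the limits differ by 14 days rests on the text alone. The flat contradiction with the 28-day sentence also assumes that the event counts as significant. The comparison by day assumes clocks that start with the hold.

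The statistical consequence is small. The Cohort 1 sample size and exact test do not involve this rule, and the number of affected subjects is probably a fraction of the 1 to 3 per 100 in the illustration. Counts of interruptions, reductions and discontinuations, and the exposure summaries, could shift slightly according to the text each site followed. The reason to act is clarity and consistency in a re-exposure decision, not the trial's main result.

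**What to change.** Reconcile the Table 2 pneumonitis row with both 4-week statements in Section 5.5, and settle the difference between those two statements at the same time. There are two neutral ways to do so. Section 5.5 can name the pneumonitis row as an exception and state whether medical monitor agreement is required, and until when. Alternatively, the row can refer to the Section 5.5 limit and its waiver. In either case, one limit should apply, its starting point should be stated, and the text should say which passage prevails. The choice of limit belongs to the sponsor's clinical team.

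The cost is about one sentence in a protocol amendment or clarification letter. The SAP needs no change. If subjects have already been held for more than 4 weeks for pneumonitis, a short listing showing the rule applied to each would let a reader interpret the interruption and discontinuation tables.
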